10.1 Definitions

The following definitions will be used in the assessment of safety:

Adverse Event (AE) is any untoward or unfavorable medical occurrence in a human subject, including any abnormal sign (for example, abnormal physical exam or laboratory finding), symptom, or disease, temporally associated with the subject's participation in the research, whether or not considered related to the subject's participation in the research.

Serious Adverse Event (SAE) is any adverse event that

- (1) results in death;
- (2) is life-threatening;
- (3) results in inpatient hospitalization or prolongation of existing hospitalization;
- (4) results in a persistent or significant disability/incapacity;
- (5) results in a congenital anomaly/birth defect; or

(6) based upon appropriate medical judgment, may jeopardize the subject's health and may require medical or surgical intervention to prevent one of the other outcomes listed in this definition (examples of such events include allergic bronchospasm requiring intensive treatment in the emergency room or at home, blood dyscrasias or convulsions that do not result in inpatient hospitalization, or the development of drug dependency or drug abuse).

Life-threatening means that the event places the subject at immediate risk of death from the event as it occurred.

Unanticipated Problem is defined as an event, experience or outcome that meets **all three** of the following criteria:

- is unexpected; AND
- is related or possibly related to participation in the research; AND
- suggests that the research places subjects or others at a greater risk of harm (including physical, psychological, economic, or social harm) than was previously known or recognized.

Possibly related means there is a reasonable possibility that the incident, experience, or outcome may have been caused by the procedures involved in the research

Unexpected means the nature, severity, or frequency of the event is not consistent with either:

- the known or foreseeable risk of adverse events associated with the procedures involved in the research that are described in (a) the protocol-related documents, such as the IRB-approved research protocol, any applicable investigator brochure, and the current IRB-approved informed consent document, and (b) other relevant sources of information, such as product labeling and package inserts; or
- the expected natural progression of any underlying disease, disorder, or condition of the subject(s) experiencing the adverse event and the subject's predisposing risk factor profile for the adverse event.

10.2 Safety Review

Both the risks listed in Section 4.1 and unknown risks will be monitored as follows:

Throughout the course of the study, all procedures and staff conduct will be monitored on an ongoing basis by each site co-investigator ([name] for prenatal clinic and the postpartum floor; [name] for pediatric clinic). Data concerning the subject accrual process, baseline characteristics of enrolled subjects, degree of maternal depression symptoms and co-morbid conditions, and health status of the infants will be monitored on a weekly basis. Investigators will meet weekly with intervention providers and research assistants to discuss all active study participants.

Monitoring will pay particular attention to adverse events or events that have the potential to become adverse. Adverse events for this study will include suicide attempts, mandatory reports to child protective services for suspected abuse or neglect, new (i.e. previously unknown) domestic violence situations, complaints from study subjects, or any instance of breach of privacy or confidentiality. In addition, we will continually monitor for worsening depressive symptoms, and activate a crisis management plan as described in the IRB protocol (attached to the INSPIR application). Each time this

protocol is activated, we will analyze if the protocol functioned as expected; if it did not, that will also be considered an adverse event. Reporting of adverse events and unanticipated problems to the BUMC IRB will be done by the study team and occur in compliance with IRB reporting policies.

[name] will meet with the site co-investigators and [name] (statistician) every two weeks to review data for the overall project. In case of an unanticipated problem or adverse event, co-investigators will notify [name] and [name] (member of the Data Safety Monitoring Board). If central monitoring uncovers an unanticipated problem based on review of the aggregate data, then [name] will alert the site co-investigators of the issue, as well as the Boston University Medical Center IRB.

Please see the Appendix for details about our Data Safety Monitoring Board (DSMB).

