6.1 Risks

Potential risks are as follows:

- Because the research covers the subject of depression, emotionally sensitive subject matter may be discussed. This may be emotionally distressing to individuals in the study.
- Although we will strive to maximize the cultural sensitivity in delivering the proposed interventions, it is possible that certain individuals' explanatory models of their conditions will be incompatible with our proposed interventions. This has the potential to upset study subjects.
- Although we will make every effort to store data in a secure and confidential manner, in concordance with IRB approval, breeches of confidentiality may occur accidentally.
- On rare occasion, information may be obtained that may require mandatory reporting (for example, if a mother divulges that her boyfriend abuses her children). Although we have developed protocols to address such scenarios, they will invariably be upsetting.

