In the inpatient setting, the first stage of screening will occur when the research staff member reviews the daily census of the postpartum unit. The research staff will review: the mother's age, maternal health insurance, maternal address, mother's phone number, and mother's past and upcoming behavioral health appointments (if available). The second stage of screening will occur when the research staff member approaches the mother per the recruitment protocol. If the mother agrees to be screened (verbal consent), the staff member will administer the EPDS in-person, as well as the verbal eligibility screen. If she scores less than a 10 or scores a 10 or greater but fails the verbal screen, she will be informed that she is not eligible for the study. If she scores a 10 or above and passes the verbal screen, she will be informed that she is eligible for the study and the study team will arrange a meeting in which written informed consent, final eligibility determination, baseline, and randomization will take place.

At the meeting for informed consent, the final stage of screening will take place. After written informed consent, study staff will administer the MacArthur Competence Assessment Tool for Clinical Research (MacCAT-CR) and a suicide screen. For safety reasons, mothers who endorse suicidality at baseline or have disordered thinking will be excluded from the study at this point. Subjects who are eligible after consent will go on to complete the baseline interview and randomization. A safety protocol for managing suicidal ideation is attached to the application.

Intervention Procedures

Following randomization, assigned providers from either intervention arm will reach out to participants to coordinate meetings. Engagement-Focused Care Coordination will entail one to two visits, lasting 45-60 minutes each. PSE will involve six visits, each lasting 30-45 minutes. Meetings for either intervention can take place at home, during a work break, or at the clinic.

Follow-Up Procedures

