Following randomization, follow-up assessments will occur every 2 months for 12 months. Follow-up assessors will be blinded to each subject's allocation. The study team will use the preferred methods of contact indicated by the subject upon enrollment (ie. phone calls, texts, email, etc). We will assess certain outcomes measures – depressive symptomatology, anxiety symptom relief, and engagement, retention, and satisfaction with mental health services – at 2 months, 4 months, 8 months, and 10 months by phone. We will assess all outcome measures at 6 months and 12 months in person. Assessment windows will be 6 weeks long: 2 weeks before the “expected date” and 4 weeks after the “expected date.” Due to the written consent form having been updated on 4/28/2018, follow-up will also include the reconsenting of participants that were enrolled and consented with the 8/10/2017 consent form.

Outcome Measure	Measured by:
Depressive symptomatology	QIDS
Symptom relief and behavioral activation	Beck Anxiety Index; Behavioral Activation for Depression Scale
Self-efficacy and coping skills	Brief COPE
Parenting Stress	Parenting Stress Index – Short Form; Perceived Stress Scale
Child behaviors	Child Behavior Checklist (CBCL-1.5/5)
Engagement, retention, and satisfaction with mental health services	Collaborative Psychiatric Epidemiology Survey; Client Satisfaction Questionnaire (CSQ-8)

10 Assessment of Safety and Data Safety Monitoring Plan (DSMP)

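### Adverse events that surface by disclosure have more chances to be found in the PSE arm, and the visible plan has no arm-neutral way of finding them, so counts by arm may be biased

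*Combined protocol and SAP*

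**What the plan says.** Section 10.2 gives a study-specific list: "Adverse events for this study will include suicide attempts, mandatory reports to child protective services for suspected abuse or neglect", followed by "new (i.e. previously unknown) domestic violence situations, complaints from study subjects, or any instance of breach of privacy or confidentiality". It adds that "we will continually monitor for worsening depressive symptoms". The stated route is a weekly meeting of investigators with both intervention providers and research assistants, covering every active participant. Section 6.1 illustrates a mandatory report with a disclosure: "if a mother divulges that her boyfriend abuses her children".

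Provider contact differs by design. Under Intervention Procedures in Section 9, "PSE will involve six visits, each lasting 30-45 minutes", whereas "Engagement-Focused Care Coordination will entail one to two visits, lasting 45-60 minutes each". Sections 5 and 8 say the six PSE sessions are weekly or biweekly.

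The contacts scheduled equally in both arms are the assessments every two months for 12 months, made by assessors blinded to allocation (Section 9, Follow-Up Procedures). The outcome table there lists no adverse event questions, and the case report forms in Section 11.3 include no form named for adverse events. Section 11.3 does list follow-up questionnaires, but their content is in attachments that are not part of the public document.

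On use of the data, Section 12.3 says under Reach that adverse events will be noted, and commits to CONSORT reporting. Section 10.3 has the DSMB reporting quarterly after reviewing the project data, and has adverse events go to the IRB in summary. Section 10.4 says there are no stopping rules. No between-arm comparison of adverse events is specified.

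**The concern.** Domestic violence enters the count only when it was previously unknown, so the count measures what staff have learned as well as what has happened. A child-protection report likewise needs someone to see or hear something that triggers it. If one arm spends several more sessions with a person who feeds the safety review, more of its events can come to light at the same true rate.

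Nothing in the visible text records who found an event, or separates events found in provider sessions from events found at the masked assessments. A reader of a by-arm table could not tell a difference in harm from a difference in observation. The error can run two ways: an apparent excess in PSE, or a real excess in the Engagement arm that goes unseen. With no stopping rules, the DSMB works by judgement on the pattern of events, so the comparability of that pattern matters. If sources are not recorded at the time, they may be hard to recover later.

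**Working it through.** The plan states no adverse event rate or safety power, so there is no figure of its own to reproduce.

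**Contacts (Section 9)**

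| | PSE | Engagement | Ratio |
|---|---|---|---|
| Provider sessions | 6 | 1-2 | 3.0-6.0 |
| Provider minutes | 6 × 30-45 = 180-270 | (1-2) × 45-60 = 45-120 | 1.5 (180/120) to 6.0 (270/45) |
| Sessions plus 6 assessments | 12 | 7-8 | 1.5-1.7 |

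**Assumptions, none of them in the documents.** True risk is equal in both arms. Each contact has the same chance h of bringing an existing event to light, whether it is a session or an assessment; h is 2-20%. All contacts take place.

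**Case A: condition already present at entry** (for example, ongoing domestic violence). Every contact can reveal it, so P(known) = 1 - (1 - h)^k for k contacts.

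| h | PSE, k = 12 | Engagement, k = 7 or 8 | Ratio |
|---|---|---|---|
| 2% | 21.5% | 13.2% or 14.9% | 1.44-1.63 |
| 5% | 46.0% | 30.2% or 33.7% | 1.37-1.52 |
| 10% | 71.8% | 52.2% or 57.0% | 1.26-1.38 |
| 20% | 93.1% | 79.0% or 83.2% | 1.12-1.18 |

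**Case B: events spread evenly over 52 weeks.** Only contacts after the event can reveal it. Assessments fall every 52/6 = 8.67 weeks. Sessions are assumed to start 1-2 weeks after randomization, so the sixth PSE session falls between week 1 + 5 = 6 (weekly) and week 2 + 10 = 12 (biweekly). After that, scheduled contact is identical in the two arms.

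Worked example with h = 10%, weekly sessions, first session at week 2. For an event after the first assessment, the chance of staying unknown contributes (0.9 + 0.9² + 0.9³ + 0.9⁴ + 0.9⁵)/6 = 0.6143 in every arm. The first 8.67 weeks add:

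- PSE: (2 × 0.9¹² + 0.9¹¹ + 0.9¹⁰ + 0.9⁹ + 0.9⁸ + 0.9⁷ + 1.67 × 0.9⁶)/52 = 0.0656. P(known) = 1 - 0.6143 - 0.0656 = 32.0%.
- Engagement, one visit: (2 × 0.9⁷ + 6.67 × 0.9⁶)/52 = 0.0865. P(known) = 29.9%.
- Engagement, two visits: (2 × 0.9⁸ + 0.9⁷ + 5.67 × 0.9⁶)/52 = 0.0837. P(known) = 30.2%.

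The ratio is 1.06-1.07. Over weekly or biweekly sessions and a start at week 1 or 2:

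| h | Ratio |
|---|---|
| 2% | 1.09-1.19 |
| 5% | 1.07-1.16 |
| 10% | 1.05-1.12 |
| 20% | 1.02-1.06 |

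**Expected counts.** With 230/2 = 115 per arm, an assumed 10% true risk (11.5 events per arm) and h = 10%, Case A gives 8.25 known events in PSE against 6.00-6.55. Case B gives about 3.6-3.8 against 3.4-3.5.

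**The case against.** The strongest reply is that the arms share most of their scheduled contact. Both have six masked assessments, research assistants attend the same weekly review, and PSE is over within about 12 weeks. An event in month 7 cannot be disclosed in a week-5 session. This stands, and it is why Case B is small.

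A reader might take the comparison of provider sessions alone, which under the same model gives ratios of about 2.1-5.7. The documents do not support that as the size of the problem, because providers are not the only route in Section 10.2. A reader might also point to the long gap that the assessment window allows ("Assessment windows will be 6 weeks long: 2 weeks before" and 4 weeks after the expected date). That gap is the same in both arms, so it is no evidence of unequal detection.

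It is fair to say, too, that contact time is not the only possible cause of a difference. Sessions can themselves give rise to complaints or privacy breaches, and those would be real effects. In minutes, the gap may be as small as 1.5-fold. The Engagement arm is steered toward formal care, where events may also surface. The net direction is likely but not certain.

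Finally, the follow-up questionnaires, the crisis management plan and the DSMB charter cannot be seen. They may already contain standard questions or a source field. This limits the point to what Section 10.2 and the rest of the visible text establish, but does not answer it.

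**Conclusion.** The point holds as a risk of unequal ascertainment, with a modest and uncertain size. Under equal true harm and an assumed 2-20% chance of disclosure per contact, the ratio of known events, PSE to Engagement, is about 1.1-1.6 for conditions present at entry and about 1.02-1.2 for events spread evenly over follow-up. Both ranges credit an assessment with the same power to reveal an event as a session; if the assessments ask nothing about these events, the ratios would be larger.

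It would be tempting to conclude that the counts will differ and that PSE will look less safe. The documents do not support that certainty. They give neither the disclosure probability nor the share of events that surface in sessions, and they plan no between-arm safety test. The bias matters only where counts are set out by arm, which is foreseeable for a DSMB and in a CONSORT report of a two-arm trial.

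**What to change.** In Section 10.2 and the follow-up questionnaires, add one fixed set of questions on the Section 10.2 events and on hospital admissions, asked in the same words in both arms at each of the six masked assessments. If the existing forms already do this, say so in Section 10.2.

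Record the source of every event: provider, masked assessment or other. In any tabulation by arm, show assessment-sourced events as the like-for-like comparison beside the all-source counts, with the number of provider contacts in each arm. Do not drop provider-sourced events. Keep session-related complaints and privacy breaches visible as possible real effects of the intervention. How events are acted on does not change.

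The cost is two or three more minutes per assessment and one field on the event log.

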10.3 Reporting Plans

The Principal Investigator at BMC/BU Medical Campus will report Unanticipated Problems, safety monitors' reports, and Adverse Events to the BMC/BU Medical Center IRB in accordance with IRB policies:

- Unanticipated Problems occurring at BMC/BU Medical Campus involving a fatal or life-threatening event will be reported to the IRB within 2 days of the investigator learning of the event.
- Unanticipated Problems occurring at BMC/BU Medical Campus not involving a fatal or life-threatening event will be reported to the IRB within 7 days of the investigator learning of the event.
- Reports from safety monitors with recommended changes will be reported to the IRB within 7 days of the investigator receiving the report.
- Adverse Events (including Serious Adverse Events) will be reported in summary at the time of continuing review, along with a statement that the pattern of adverse events, in total, does not suggest that the research places subjects or others at a greater risk of harm than was previously known.
- Reports from safety monitors with no recommended changes will be reported to the IRB at the time of continuing review.

The Principal Investigator will report Unanticipated Problems and Adverse Events to the BUMC IRB and to the study's Data Safety Monitoring Board (DSMB).

The DSMB will communicate its reports and recommendations on a quarterly basis after reviewing comprehensive project data. The DSMB will furnish a letter with its recommendations to [name].

10.4 Stopping Rules

The study has no stopping rules.

11 Data Handling and Record Keeping

11.1 Confidentiality

All subjects will be assigned a unique study code. We will maintain subject confidentiality in the following ways:

1. The cross-walk that links study codes with identifying information will be kept in a secure network location and in a REDCap database. There will be 2 separate REDCap databases: one solely for identifying information and one solely for study data.
2. We will be using REDCap, a database intended for large research studies which can securely manage HIPAA-sensitive data.
3. All subjects will be made aware that no one from the clinical staff (aside from those directly involved in the study) will have access to any information.
4. All intervention sessions will take place in private areas.
5. Subjects will be given options to maintain confidentiality during contact. For example, if it is okay to leave a message and what specifically to say during the message from study staff to maintain confidentiality.

The study monitor or other authorized representatives of the sponsor may inspect all documents and records required to be maintained by the investigator, including but not limited to, medical records (office, clinic, or hospital) and pharmacy records for the subjects in this study. The clinical study site will permit access to such records.

11.2 Source Documents

The only source data/document needed for this study that is part of the subject's standard of care treatment outside of the research is the EPDS screen. Responses will be entered by potential subjects either physically (on paper) or electronically (ie. on an iPad), depending on clinic resources. These results will later be entered into the subjects' EHR by clinic staff.

All other study data will be obtained directly from subjects by study staff at study visits.

11.3 Case Report Forms

The study case report form (CRF) will be the primary data collection instrument for the study. All data requested on the CRF will be recorded. All missing data will be explained. If a space on the CRF is left blank because the procedure was not done or the question was not asked, "N/D" will be written. If the item is not applicable to the individual case, "N/A" will be written. All entries will be printed legibly in black ink. If any entry error has been made, to correct such an error, a single straight line will be drawn through the incorrect entry and the correct data will be entered above it. All such changes will be initialed and dated. There will be no erasures or white-out on CRFs. For clarification of illegible or uncertain entries, the clarification will be printed above the item, then initialed and dated.

Please see the Study Attachments in INSPIR for the following CRFs:

- Edinburgh Postnatal Depression Scale (EPDS)

- Suicide Screen
- MacArthur Competence Assessment Tool for Clinical Research (MacCAT-CR)
- Baseline Questionnaire
- Follow-up Questionnaires
- Collaborative Psychiatric Epidemiology Survey
- Child Behavior Checklist
- Parenting Stress Index Short Form
- Brief COPE
- Behavioral Activation for Depression Scale
- Beck Anxiety Index
- QIDS
- Verbal eligibility screen
- PSE Worksheet
- MINI (Mini International Neuropsychiatric Interview)

11.4 Study Records Retention

We will retain study records for at least 7 years after the completion of the study. We will retain documentation of informed consent for at least 3 years after completion of the study, after which we will shred or permanently delete such documentation.

12 Statistical Plan

12.1 Study Hypotheses

Given PSE's penetrance and acceptability in prior studies [21-23], we hypothesize that its uptake will exceed 85% among women in this comparator; that it will provide sustained symptom relief; and that it will prevent the need for referring certain mothers (i.e. those with subsyndromal depression) to more formal care. By virtue of improved coping skills and behavioral activation, we hypothesize that PSE will make referrals to formal care more effective (for those who need it) than Engagement Interviewing alone. However, it is also important to assess the possibility that PSE may represent an unnecessary step that only serves to delay more definitive care and symptom relief. Our ultimate goal is to reduce disparities in access to mental health care for low-income mothers; and to improve outcomes for them and their children.

12.2 Sample Size Determination

Sample Size. For this project, our results would be used to build a case for intervention implementation within the PCMH. Because small differences in outcomes would fail to make this case effectively, we aim to detect a 33% relative reduction in symptomatic depressive episodes (defined as a bimonthly QIDS score ≥ 11) – which is both clinically important and consistent with previous work. All estimates assume 80% power and a two-sided alpha of 0.05.

1. **Incident rate of moderate to severe symptomatic episodes.** Using Poisson regression analysis, with 100 analyzable subjects in each study group and a Poisson rate of 1.2 symptomatic episodes per 6 follow-up assessments in one group (gleaned from data among a demographically similar population of peripartum women), we can detect a 33% reduction in the rate of episodes to 0.8 in the other group.
2. **Depressive symptoms over time.** In prior longitudinal data, we have observed the following mean QIDS scores for each follow-up month and assume these values for one group in the planned study: 8.2; 7.6; 7.5; 6.9; 7.2 (common SD, 5.9). We hypothesize that the following mean QIDS scores in the other group would be achievable and clinically significant: 7.2; 6.6; 5.5; 4.4; 4.2, resulting in a mean difference of 3 points at the final study time point in QIDS scores across study groups (note: a 3-point difference in QIDS scores, in the majority of cases, would move a subject across a clinical cutoff corresponding to mild, moderate or severe symptoms). Using a two-group repeated measures design analyzed by generalized estimating equations or mixed linear models, noting within-subject correlations of 0.7 for values separated in time by one month and 0.6 for those separated for two months or more in our longitudinal analysis, we can detect the above differences in the means between groups over time with 100 subjects per study group with 89% power for a correlation of 0.7 and 77% for correlation of 0.6.
3. **HTE analysis.** If we assume that equal numbers of women will be recruited pre- and postnatally, 100 subjects per arm will provide 86% power to detect differential effects of treatment between pregnant and postpartum women as extreme as a rate ratio of 0.38 in the prenatal stratum (rate in one group=0.45 vs. rate in the other=1.2) compared to a rate ratio of 0.96 in the postpartum stratum (rate in one group=1.15 vs. rate in the other=1.2).

Therefore, with an analyzable sample of 100 subjects per study group, we will be able to detect with adequate statistical power differences in incident rates of elevated QIDS scores and mean QIDS scores over time that are of clear clinical relevance. Based on our current data, we estimate that 20% of mothers with positive EPDS screens will refuse participation; 77% will meet full eligibility criteria; and we will experience a 15% attrition rate over the course of the study. Therefore, to ensure that we assess outcomes in 200 study subjects, we will approach 374 mothers with depressive symptoms and randomize 230. This sample size will be readily available from our two clinic sites.

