4.2 Study Outcome Measures

4.2.1 Primary Outcome Measures

Each subject will have 12-months of follow-up. All outcomes will be assessed at 2-month intervals.

Our primary outcome measure is depressive symptomatology, as measured by the QIDS – and operationalized as an incident rate of moderate to severe episodes over time and as symptom trajectories.

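### The 80% power for the episode rate and 86% for the timing interaction assume Poisson variance; with the plan's own QIDS correlation of 0.6 they fall to about 45% and 52% under a latent-normal model (about 40–70% and 45–66% across models).

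*Combined protocol and SAP*

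**What the plan says.** Section 4.2.1 gives the QIDS primary outcome two forms: it is "operationalized as an incident rate of moderate to severe episodes over time and as symptom trajectories". Section 12.2 then makes three power statements, all with 100 analysable women per arm and a two-sided alpha of 0.05.

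- **Item 1, episode rate.** "Using Poisson regression analysis, with 100 analyzable subjects in each study group and a Poisson rate of 1.2 symptomatic episodes per 6 follow-up assessments". The comparison arm's rate is 0.8, and the target is 80% power. The event counted is "symptomatic depressive episodes (defined as a bimonthly QIDS score" of 11 or more.
- **Item 2, mean scores.** This item uses a within-woman correlation, "noting within-subject correlations of 0.7 for values separated in time by one month and 0.6 for those separated for two months or more", and reports its power "with 100 subjects per study group with 89% power for a correlation of 0.7 and 77% for correlation of 0.6".
- **Item 3, heterogeneity of treatment effect (HTE) by timing.** "100 subjects per arm will provide 86% power to detect differential effects of treatment between pregnant and postpartum women", from rates of 0.45 against 1.2 prenatally and 1.15 against 1.2 postpartum.

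The closing paragraph of 12.2 concludes that power is adequate for episode rates as well as for mean scores. Section 9 (Follow-Up Procedures) sets the schedule: "follow-up assessments will occur every 2 months for 12 months". Section 12.3 (Main Effects) allows Poisson or negative binomial regression for the episode rate and gives no rule for choosing. Its remark that dispersion will guide the choice is attached to the number of mental health visits, not to this outcome.

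**The concern.** A woman's episode count is not a Poisson count of separate events. It is the number of her six scheduled assessments, 0 to 6, at which the QIDS is at or above a cutoff. If scores persist within a woman, some women are above the cutoff at most visits and many at none, so the variance of the count exceeds its mean. The plan's own correlation of 0.6 applies to every pair of visits two months or more apart, which is every pair in this schedule. Item 2 uses it; items 1 and 3 do not.

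Two things are at stake. If power is nearer one half than 80%, a null result on the episode rate or on the timing question cannot be read as ruling out the targeted effect. And if the same variance assumption enters the analysis through model-based Poisson standard errors, false positives become too frequent.

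**Working it through.** **Inputs from the plan.** 100 per arm; rates 1.2 and 0.8 per six visits, so p = 0.20 and 0.133 per visit; two-sided alpha 0.05; HTE rates 0.45, 1.2, 1.15 and 1.2 with equal strata, so 50 women per cell; score correlation 0.6; item 2's means and SD of 5.9.

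**1. The plan's figures (variance = mean).** Wald test on the log rate ratio:

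- Main effect: SE = √(1/120 + 1/80) = 0.144; ln 1.5 = 0.405; power = Φ(0.405/0.144 − 1.96) = 80.2%.
- HTE: ln(0.375/0.958) = −0.938; SE = √[(1/50)(1/0.45 + 1/1.2 + 1/1.15 + 1/1.2)] = 0.3085; power = Φ(0.938/0.3085 − 1.96) = 86.0%.

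Both reproduce.

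**2. Correlated visits, no latent model.** With r the correlation between a woman's yes/no results at two visits, Var(count) = 6p(1−p)(1+5r). At r = 0 the variances are 0.96 and 0.693, so SE² = 0.96/(100×1.2²) + 0.693/(100×0.8²) = 0.0175. With a common r, SE² = 0.0175(1+5r).

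| r | Main effect | HTE |
|---|---|---|
| 0 | 86.5% | 90.7% |
| 0.1 | 70.6% | 76.4% |
| 0.2 | 58.2% | 64.0% |
| 0.3 | 49.1% | 54.6% |

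For the main effect, 80% needs r ≤ 0.039. For HTE, the stated 86% needs r ≤ 0.033, and 80% needs r ≤ 0.074.

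**3. From score correlation to r.** This step needs a distributional assumption that the plan does not give. Assume a latent-normal score with equal correlation between all visits, cut so that the mean count equals the planned rate. At 0.6, r = 0.370 (p = 0.20) and 0.343 (p = 0.133):

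- Variances: 0.96(1 + 5×0.370) = 2.74 and 0.693(1 + 5×0.343) = 1.88, which are 2.28 and 2.35 times the means.
- Main effect: SE = √(2.74/144 + 1.88/64) = 0.220; power = Φ(0.405/0.220 − 1.96) = 45.3%.
- HTE: SE = 0.468; power = Φ(0.938/0.468 − 1.96) = 51.8%.

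| Score correlation | Main effect | HTE |
|---|---|---|
| 0.2 | 71.2% | 78.1% |
| 0.3 | 63.8% | 71.2% |
| 0.6 | 45.3% | 51.8% |
| 0.7 | 40.3% | 46% |

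The main effect reaches 80% only at a score correlation of about 0.09 or less; HTE reaches its stated 86% only at about 0.08 or less. The rate ratio detectable with 80% power is 0.51 at 0.6 and 0.60 at 0.3, against the stated 0.67. At the expected 230 × 0.85 / 2 = 97.75 per arm, the main-effect figures move by under one point (79.3% and 44.5%).

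**4. Other assumptions at 0.6, main effect.**

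- Skewed (gamma) scores at the planned rates: 40–42% (HTE 45–47%).
- Multivariate t scores: 43%.
- Correlation decaying with the gap (AR(1)): 58% (HTE 66%). This is generous, because the plan gives a flat 0.6 for all gaps of two months or more.
- Item 2's means and SD, normal scores, fifth mean carried to visit 6 (the plan lists five): 68.5% with the cutoff at 11 and 70.4% at 10.5. These imply 1.64 against 1.04 and 1.81 against 1.18 episodes. At a correlation of 0.3 the same set-up gives 86–88%.
- Item 2's control means with a one-third cut at every visit: 59–65%.
- Item 2's means with gamma scores: 50–55%.

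**5. Choice of analysis.** Simulation, 4,000 trials per setting, latent normal at 0.6, main effect:

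| Analysis | Rejects at 1.2 v 0.8 | Type I error |
|---|---|---|
| Poisson, robust variance | 47% | 4.9% |
| Negative binomial | 41% | 3.2% |
| Poisson, model-based variance | 72% | 19% |

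The 19% agrees with a direct calculation: 1.96/√2.28 = 1.30, and 2(1 − Φ(1.30)) = 0.19. For HTE, type I error was 5.1% robust and 20% model-based.

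**The case against.** The stated figures contain no slip of calculation; the dispute is over a variance assumption. The best arguments for the plan are these.

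- **The 45% is model-dependent and near the low end.** It needs latent normality and equal correlation, and it carries a correlation from one set of prior data to a rate that may come from another. Item 2's treated-arm means ("We hypothesize that the following mean QIDS scores in the other group would be achievable and clinically significant: 7.2; 6.6; 5.5; 4.4; 4.2") with the stated SD give up to 70% at 0.6, and over 80% at 0.3. This stands as a reason to report a range. It does not rescue the 80%: 0.6 is the plan's own value, nothing run at 0.6 reaches 80%, and the most favourable case assumes more episodes than item 1 does. Normal scores with those means also fit poorly; at a mean of 4.2, about 24% would lie below zero.
- **Negative binomial is already permitted, and model-based standard errors are never specified.** True. But negative binomial protects type I error without restoring power, and the plan neither excludes model-based Poisson nor says when to leave it. The general sentence on unmet distribution assumptions commits only to considering alternatives.
- **Baseline adjustment could recover power.** In the same latent-normal model, adding a baseline score to robust Poisson raised simulated power from 47% to 64% (1,500 trials, type I error 6.1%). The plan does not specify this adjustment, selection on EPDS of 10 or more would shrink the gain, and 64% is still below 80%.
- **The trajectory form has its own power statement that uses the correlation.** It does, and it is not questioned here. The episode rate is nevertheless a named form of the primary outcome, and 12.2 claims adequate power for it.

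**Conclusion.** The point holds. The 80% and 86% require the episode count to have Poisson variance or less, and the plan's episode definition, visit schedule and stated score correlation together contradict that. The direction needs no latent model: a yes/no correlation between visits above about 0.04 takes the main comparison below 80%. The size does need one. Under a latent-normal score at 0.6, power is about 45% for the episode rate and 52% for HTE; the other assumptions run at 0.6 span about 40–70% and 45–66%. The plan gives no dispersion for the counts, so no single corrected figure can be read from it. The observed variance of the per-woman counts behind the 1.2 rate, if the sponsor has it, would settle the matter better than any conversion.

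**What to change.** 1. **Restate the power in 12.2, items 1 and 3.** At a score correlation of 0.6, give about 45% for the episode rate (about 40–70% across stated assumptions) and about 52% for HTE (71% at a correlation of 0.3). Say that the single figures rest on a latent-normal conversion, and give the detectable rate ratio, about 0.5–0.6. If the per-woman counts behind the 1.2 rate are available, use their observed variance instead.
2. **Amend the closing paragraph of 12.2** so that it no longer claims adequate power for episode rates.
3. **Fix one overdispersion-robust analysis in 12.3**, for both the main effect and HTE: for example, Poisson regression with sandwich variance and log(completed assessments) as offset. Rule out model-based Poisson standard errors. This controls error; it does not restore power.

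The cost is wording only, with no extra patients. The sponsor accepts a less favourable stated power and gives up the apparent 72% of model-based Poisson, which comes with 19% type I error.
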